6.3.2 Sample size

Our sample size estimates are based on previous high and low transmission season surveys conducted during the first ICEMR (2010–2017) in areas similar to the clusters that will be selected for this study. Based on these data, we anticipate that 13%-18% of households will contain a child 7-18 months old. The risk of infection in this age group is estimated to be 21% (30% high and 20% low transmission seasons). In children \leq 10 years of age the risk of infection is estimated to be 31% (46% in the high and 32% in the low transmission seasons). The within-cluster correlation is estimated at 0.004 (0.05 in the high and 0.00 in the low transmission seasons) and 0.14 (0.22 in the high and 0.06 in the low transmission seasons) for children aged 7-18 months and \leq 10 years of age, respectively. Based on these data, by studying the 25 clusters with 20 households with a child 7-18 months per intervention arm, we will analyze 500 children aged 7-18 months and a similar or larger number of older children. For power calculations, we assumed that these proportions represented the risk of incident cases of infection.

This proposed sample size will allow us to estimate moderate effectiveness of the combined interventions (versus no intervention) with 80% power in 2-sided tests, accounting for within-cluster correlation, and with α -level of 0.05. For instance, based on the cross-sectional estimations of individual risk of malaria infection obtained at enrollment of each cohort, we will be able to

detect the effectiveness of 34% (36% and 33% when stratifying by season) in children 7-18 month-old (Hayes, 2009). In a repeated measure analysis, with within-subject correlation of 1.5 to 2 times larger than within-cluster correlation, we will be able to detect effectiveness of 34-37% in children 7-18 month old (Liu, 2002).

For entomological assessments, 100 households from each of the two arms will be visited for entomological analysis including *Anopheles* abundance, female mosquito parity, and source of blood meal and sporozoite prevalence. Based on our previous experience, we have found an average of one *Anopheles* mosquito per household sampled (although with very heterogeneous distribution), and 75-95% human-biting prevalence.

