Molecular analyses: At enrollment and at every two-month visit, we will collect finger-prick blood samples from all enrolled participants. These specimens will be used to assess *P. falciparum* infection by quantitative PCR. Then the specimens will be stored for later determination of gametocyte-specific gene expression and gametocyte density. Serum will be collected to assess for serological evidence of exposure to infection and response to vaccination.

Household mosquito collection and testing. Vector populations will be sampled from 100 study households (from RTS,S age-eligible households) in both intervention arms. The selection of the households for mosquito collection will be done during the recruitment of age-eligible children. In each catchment area CDC miniature light traps will be set in sleeping rooms to capture host-seeking vectors indoors. We will also sample blood-fed and gravid mosquitoes by indoor aspiration and exit trap sampling. Sampling will occur at each house on four consecutive nights during the last four weeks of the rainy season to optimize catch numbers. Light traps will be set up in a single functional bedroom in each of the households. Local personnel in each catchment area will be trained to carry out these procedures.

Species of captured adult mosquitoes will be determined by visual examination under microscopy and PCR-based assays using procedures well established in our laboratories. Blood-fed mosquito abdomens will be tested for the host species that were fed upon using a PCR method based on the vertebrate mitochondrial cytochrome B gene. The separated thorax and head of each female will be tested for salivary gland *P. falciparum* sporozoites using standard ELISA or PCR to estimate infection prevalence. For non-blood fed mosquitoes, we will assess their parity status by dissection and examination of mosquito ovaries.

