To examine antibodies of exposure, two approaches will evaluate the association between levels of exposure antibodies and intervention groups: 1) antibody levels will be summarized using partial least square regression (PLS); 2) levels of individual antibodies will be used. Summary scores and antibody levels will be compared over time between the two groups through joint outcome (shared parameter) models (Verbeke, 2010). Moreover, joint outcome models will be fit for positivity of responses and a zero-inflated model will be fit for the breadth of responses (number of antibodies that are positive in a subject).

For analysis of effectiveness in all household members (in Phase 1, children aged >18 months and \leq 10 years old), indirect effectiveness at the individual level at four-time points will be estimated. Also, in nested random effect models for individual analysis, we will account for correlation across visits, within the household. The household-level analysis will be conducted by summarizing outcomes in the household, and also in nested random effect models, using the same link functions described above.

For entomological outcomes, analysis of effectiveness will be performed comparing intervention groups through zero inflated negative binomial models with random effects, including as offsets hours of capture effort or number of captured mosquitoes, as appropriate. Outcome variables will include abundance of *Anopheles*, sporozoite rates, blood-meal originated from humans, and female parity in households.

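### Human blood meal and parity are scored in separate parts of the mosquito catch, but the planned count model gives neither outcome its own denominator

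*Combined protocol and SAP*

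**What the plan says.** Section 6.5 (Analysis Plan) compares the arms on entomological outcomes with "zero inflated negative binomial models with random effects, including as offsets hours of capture effort or number of captured mosquitoes, as appropriate". The outcomes sent through that model are abundance, sporozoite rates, "blood-meal originated from humans, and female parity in households".

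Section 6.4 (household mosquito collection and testing) defines who is scored for what:

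- Host blood: "Blood-fed mosquito abdomens will be tested for the host species that were fed upon".
- Parity: "For non-blood fed mosquitoes, we will assess their parity status by dissection and examination of mosquito ovaries".
- Sporozoites: every female is tested.

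The catch comes from several methods. Light traps target host-seeking vectors, and the plan adds: "We will also sample blood-fed and gravid mosquitoes by indoor aspiration and exit trap sampling". Section 6.5 does not say whether these catches are pooled.

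Section 6.3.2 lists "female mosquito parity, and source of blood meal and sporozoite prevalence" among the entomological assessments and gives 100 households per arm. No section names the number typed or the number dissected as an offset or a binomial denominator.

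**The concern.** The blood-fed and non-blood-fed mosquitoes are two non-overlapping parts of the catch. Hours suit abundance, and captured females roughly suit sporozoite rate, which is not part of this point. Neither offset fits the other two outcomes.

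Per captured mosquito, the blood-meal model estimates human share times blood-fed share, and the parity model estimates parous share times one minus blood-fed share. The arms have different nets, and the blood-fed share also depends on the mix of trap methods if catches are pooled, so a difference in that share is plausible. Per hour, abundance enters both models as well, and section 3.2 reports that PBO nets affected *Anopheles* density in the cited trial.

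The analysis could therefore show less human feeding when host choice is unchanged, or hide a real fall in parity. Section 6.1 counts entomological evidence among the impacts sought and links the application for a larger study to significant results, without saying which entomological outcomes count.

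**Working it through.** The plan states no power or precision for any entomological outcome, so there is no figure of its own to reproduce.

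**Inputs from the documents.** 100 households per arm; on the catch, "we have found an average of one" *Anopheles* per household sampled; human-biting prevalence 75-95% (all 6.3.2). Also, "Sampling will occur at each house on four consecutive nights" (6.4). The mean catch is therefore taken as 1 per house, or 4 if the figure of one is per night.

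**Assumptions.** Blood-fed share f, human share h = 85%, parous share p = 60%, and catch dispersion k = 0.3 and 1. Arm 1 is the intervention arm and arm 0 the control arm.

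**Expected ratios.**

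- Captured offset: blood meal = (h1 × f1)/(h0 × f0); parity = p1(1 − f1)/[p0(1 − f0)].
- Hours offset: each of these multiplied by the abundance ratio.

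With h and p equal in both arms, the true ratios are 1. The captured offset gives:

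- f = 25% v 30%: 0.25/0.30 = 0.83 and 0.75/0.70 = 1.07.
- f = 20% v 30%: 0.20/0.30 = 0.67 and 0.80/0.70 = 1.14.
- f = 20% v 40%: 0.20/0.40 = 0.50 and 0.80/0.60 = 1.33.

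These do not depend on where h lies within 75-95%.

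**False rejection, captured offset.** Simulation: 10,000 runs, gamma-Poisson catches, Poisson log-ratio with offset (the lower-variance limit of the negative binomial), Wald test at 5%, no within-house correlation of outcomes. Entries are model-based / household-robust; ranges cover both values of k.

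| Mean catch | f, arm 1 v arm 0 | Blood meal | Parity |
|---|---|---|---|
| 1 | 25% v 30% | 6% / 10-11% | 2% / 7-8% |
| 1 | 20% v 30% | 21-22% / 30-32% | 3-4% / 14-15% |
| 1 | 20% v 40% | 67-68% / 78% | 18-20% / 40-41% |
| 4 | 25% v 30% | 20% / 30-31% | 4% / 14-15% |
| 4 | 20% v 30% | 75-77% / 83-84% | 17-18% / 40-41% |

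A binomial score test on the tested mosquitoes rejects in 4.5-5.4% throughout. A separate run (1,000 trials, k = 0.5, mean 1) with a control share of 50% gave blood-meal ratios of 0.80, 0.60 and 0.50 for intervention shares of 40%, 30% and 25%. Robust false rejection was 24%, 73% and 90%, against 5.5% at equal shares.

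**A masked effect.** Take a true parity fall from 70% to 52.5% with f = 20% v 40%. The ratio is (0.525 × 0.80)/(0.70 × 0.60) = 0.42/0.42 = 1.00. It is detected in 1% (model-based) or 5-6% (robust) of runs, against 55-56% (mean 1) or 98-99% (mean 4) with the binomial test.

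**Hours offset.** With abundance 0.6 v 1.0 per house and equal shares, both ratios are 0.60. Robust false rejection is 23-27% for blood meal and 32-45% for parity. If f is also 20% v 30%, the ratios are 0.6 × 0.20/0.30 = 0.40 and 0.6 × 0.80/0.70 = 0.69.

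**Power when blood-fed shares are equal** (mean 1, so no bias):

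| f in both arms | Feeding 90% v 70%: captured, robust | Same: binomial | Parity 50% v 70%: captured, robust | Same: binomial |
|---|---|---|---|---|
| 20% | 12% | 35% | 61% | 73-74% |
| 30% | 16-17% | 50% | 50-52% | 67% |
| 40% | 22-23% | 61-62% | 41% | 59-60% |

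**If the offset is read as mosquitoes tested.** The bias disappears. However, a Poisson-type variance for a high proportion p overstates the standard error by √[1/(1 − p)] when outcomes are not clustered: √(1/0.25) = 2.00 at 75% and √(1/0.05) = 4.47 at 95%. Power for 90% v 70% is then 0.3-1.7% with model-based standard errors. With robust ones it is 31-33%, 47-48% and 60% at the three blood-fed shares.

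**The case against.** The strongest reply is that one sentence covers four outcomes and ends by leaving the choice of offset to what is appropriate. A sensible analyst would use hours for abundance and, for blood meals, the captured mosquitoes that were typed. The team's own 75-95% human-biting figure points that way: as a share of a whole catch it would need at least 75% of mosquitoes to be blood-fed. On this reading the bias goes, and robust standard errors recover nearly all the power.

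That reading is possible, but it is not what the text says. The qualifier chooses between two named offsets and adds no third. Nor does the reading rescue the count model with model-based errors, and section 6.5 does not mention robust ones.

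Other points stand as limits:

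- Every size depends on assumed shares. At 25% v 30% and one mosquito per house the distortion is small.
- The masked parity fall was chosen to cancel exactly.
- The simulation is a Poisson stand-in without zero inflation or random effects. The expected ratios do not depend on that, but the percentages do.
- The parity formula assumes every non-blood-fed mosquito is dissected and scored.
- The hours case deserves less weight, since the same sentence offers a per-mosquito offset. Human-fed mosquitoes per hour would be a legitimate outcome, but the plan does not name it, and that reading does not help parity.
- Both outcomes are supporting: they are absent from Table 1, the study is preliminary, and the raw counts can be reanalysed.

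**Conclusion.** The concern holds. As written, neither listed offset is the denominator of human blood meal or of parity. That the captured offset moves the two ratios in opposite directions when blood-fed shares differ is algebra and needs no assumption. How far they move does: from negligible at 25% v 30% with one mosquito per house to a spurious halving of the blood-meal ratio at 20% v 40%. With equal shares nothing is biased, but power for the human-feeding contrast falls to well under half that of the binomial analysis. The point should be corrected. It concerns supporting outcomes and does not touch abundance, sporozoite rate or the infection endpoints in children.

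**What to change.** In section 6.5:

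- Keep the zero-inflated negative binomial with the effort offset for *Anopheles* abundance. Sporozoite rate may stay as planned.
- Analyse human blood meal among blood-fed females typed, and parity among non-blood-fed females dissected, each with a binomial (logistic) model.
- Allow for household clustering by a household random effect or, where catches are too sparse to estimate one, by household-robust standard errors.
- Report the blood-fed share by arm and trap type.
- If human-fed mosquitoes per catch or per hour is of interest, name it as a separate outcome.

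The cost is a few sentences and slightly more analysis, with no new data or procedures. The fallback is needed: at one mosquito per house and 20-40% blood-fed, only about 3-9 of 100 households per arm would hold two or more typed mosquitoes (about 18-38 at a mean of 4).

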6.5.1 Data handling and record keeping

Data for the survey will be collected through questionnaires programmed onto computer tablets. Electronic records (in the form of structured questionnaires) will be made from each data-producing contact between the study participants and the study team. These source data are de-identified (each sheet containing date, participant number, household number and signature of the data collector). Questionnaires will be administered to household owners by enumerators. Every day after the fieldwork the questionnaires will be uploaded loaded to a secure central database. The team leader/ data manager will immediately check for errors. Additionally, periodic reports will check for errors in data capture. The database will be managed at the Data Management Core at the College of Medicine in Blantyre. All documentation regarding the participants will be identified with appropriate participant codes, both on paper and in computer files. Samples will be de-identified and contain only a sample identification code. The names will only appear on informed consent forms and a separate coding list that will be secured stored, separately from the database. Only the Principal Investigators and designated study personnel

will have access to the code list linking study identification numbers with the subject identifiable information.

The investigators shall maintain the records of their copies of the questionnaires and regulatory documents (informed consents, ethical approval) with all records kept in a secure place. Clinical information will not be released without written permission of the subject, except as necessary for monitoring.

6.6 Results presentation and dissemination

The results of this study will be presented through tables, graphs and powerpoint presentations. If maps are used to display information about malaria prevalence, household GPS data will be aggregated at the village or cluster level such that individual households are not identifiable. Locally, the results will be discussed with the villages in the study area, the health centers involved, Machinga and Balaka District Health Office and Assembly. The main findings will also be published in international peer-reviewed journals and the Malawi Medical Journal, and through presentations at local, regional or international conferences/seminars. Results will also be presented to the College of Medicine Research and Ethics Committee (COMREC) and the National Malaria Control Program since they develop and implement policy as well as other stakeholders.

Data will be collected prospectively and this data will be of use to the Malawi National Malaria Control Program, NIH and other malaria control partners in Malawi and beyond. Data from studies will be made available to researchers, policymakers and the wider community at no cost to promote dialogue on the results, encourage further analysis, inform new research questions and disseminate information to the community. This data sharing plan is designed to enable access to as much data as possible while protecting the human subject identity and ensuring proper use.

De-identification of data:

Under this proposal, we will de-identify all the data intended for broader use and variables which could be used to deductively disclose the identity of individual subjects. Examples of data that will be removed include names, date of births or attendance at clinics, medical record numbers, GPS location etc. Only the PI and designated personnel in Malawi will have access to the link between study and sample identification number and the names and medical record numbers of study participants. Only staff and investigators with authorization from the

Data Sharing:

All de-identified data will be made available through NIH supported portals for wide dissemination and access. All de-identified human clinical and epidemiological data will be available through the ClinEpiDB repository whilst genomic data from humans (if any) and mosquitoes will be made available through controlled access to the EuPathDB repository. Any data shared will be subjected to conditions of use governing access to the public release data, including restrictions against attempting to identify study participants, destruction of the data after analyses are completed, reporting responsibilities, restrictions on redistribution of the data to third parties, and proper acknowledgment of the data resource.

Data Submission and Release Timeline:

Research data from a completed study will be shared with the scientific community and other interested organizations within a period of one year from completion of the study when the data has been thoroughly cleaned and a draft report has been written. Data will be sent to the repositories no later than the closure date for the grant.

7 ETHICAL CONSIDERATIONS

7.1 General Principles

Strict measures will be taken by the study investigators and study staff members to ensure subject confidentiality. The study protocol, documentation, data and all other information generated will be kept in strict confidence. Each participant will be assigned a unique Participant Identification Number (PID) that will be used for data entry and analysis linked to the different Case Report Forms (CRFs). Records will only be accessible to the data entry team, the individual conducting data entry checks as part of the dual entry system and the authorized study investigators. All consent forms containing identifiable information will be kept in a locked cabinet available only to the Principal Investigator. All data will be stored in and analyzed using password-protected, encrypted secure computers. No information or data of the study participants will be released to any unauthorized third party without prior approval of the study participant and appropriate IRBs. If maps are used to display information about malaria prevalence, household GPS data will be kept in a separate file (to which only the PI and designated personnel involved in data captures will have access).

7.2 Informed Consent

Consent will be sought from all collectors and study participants. Informed consent will be initiated by the study staff prior to anyone agreeing to participate in the study. The study staff members will introduce themselves and explain the purpose of the study to the parent/guardian. In this study, a guardian or caretaker will be defined as any adult of legal age with a blood relation to the child (such as a grandparent, sister or aunt) or a legal guardian who is involved in taking care of the child. The parent/guardian of potentially eligible children will then be asked to read the informed consent in the preferred language either in Chichewa (the local language) or in English. The informed consent will be read and explained verbally in Chichewa to those who are unable to read. This verbal explanation will be attended by an impartial witness who will also sign the consent form. If no impartial witness is available, a member of the study staff other than the person administering consent may serve as a witness and sign the document. Study staff members will then answer any questions that the parent/legal guardian of the child participant may have, following which they will be asked to sign the informed consent form. For those who cannot write, a thumbprint will be placed on the form, with the signature and the date of the witness. A copy of the consent form will be given to the parent/guardian. All consent forms will be IRB approved in Malawi and the USA.

Study participation will be completely voluntary and participants will be informed that they may withdraw consent at any time throughout the course of the study without penalty. The rights and welfare of participants will be protected by emphasizing to the parent/guardian that the quality of the participant's medical care will not be adversely affected if they decline participation. If the parent/guardian decides to withdraw consent, the participant/child will be able to continue to receive health care at the government clinics and hospitals or wherever they choose.

Future Use of Stored Specimens:

The informed consent form for this study has a section that will offer participants a choice about the use of study specimens that remain after the study procedures have been completed. Any use of study samples that is outside the scope of this protocol will be submitted for prior review and approval by the appropriate IRBs when the need arises. Only blood samples collected during finger pricks will be stored for possible future use either as dry blood spots on filter paper or as plasma or serum in cryovial tubes.

7.3 Possible risks and benefits to study participants

7.3.1 Potential Risks

Fingerprick blood sampling: All participating children will be screened for Plasmodium infection during monthly visits, and for disease during unscheduled visits to the HC when they have any illness. Plasmodium infection screening will be done through a routine monthly sample taken for dried blood spots (DBS). Blood samples for all these procedures will be done through a finger prick which may cause participants temporary discomfort. Moreover, blood specimens collected through finger prick will be used to measure serological markers. However, this will also represent a negligible volume of blood collected through finger prick. To prevent any discomfort and risks associated with finger pricks, we will use optimal lancets and will appropriately clean the area before the extraction of blood.

Breach of confidentiality: All data collected during the survey is strictly confidential. There is however a small risk of breach of confidentiality during the study with inadvertent access of personal health information to non-study personnel. Efforts directed to reduce this risk will be a priority by having all study data coded. Each participant will be given a unique Participant Identification number (PID), and all electronic data will be linked to this PID. Directions to the house of the participant will be linked to the PID. It will however, be accessible by the home interviewer only during home interviews and by Data Managers to address queries. All field data collection will be done on PDAs that will be password protected and accessible only to the relevant study personnel staff. Data recorded in the PDA will be transferred to the main data base at the end of each day.

All electronic data will be stored in password-protected computers in a locked room in the data management Core section (DMC). The password protected database files will only be accessible to designated data entry personnel and study investigators. Backup copies of the database files will be maintained in a separate hard disk that will be kept in a locked filing cabinet at DMC. The dataset mapping PID to subject identifiable information including names and directions to the households will be stored separately from the research database and only the PI and the essential research team will be granted access to this dataset.

Compensation: In accordance with the Malawi National Commission for Science and Technology (NCST) circular dated 22nd August 2019, we will reimburse the parent/guardian (household) with MK 2,000 for the travelling costs each time she/he comes with participants to the central location for blood sample collection and interviews. The amount of money to be reimbursed is an estimated average cost for participants who travel to and from the designated central location.

